9. MECHANISTIC ASSAYS

9.1 MECHANISTIC HYPOTHESES

The main mechanistic hypotheses being tested are whether combination of dupilumab with *Phleum pratense* SLIT will result in:

1. Down-regulation/deletion of grass pollen-driven Th2 responses in peripheral blood, nasal fluid and nasal epithelial cells.
2. Immune deviation in favor of grass pollen-driven Th1 responses in peripheral blood, nasal fluid and nasal epithelial cells.
3. Induction of grass pollen-driven regulatory responses in peripheral blood, nasal fluid and nasal epithelial cells.
4. Changes in downstream events, including:
 - a. Reduction in allergen-specific IgE in sera or plasma.
 - b. Development of allergen-specific IgG, IgG4, and IgA antibodies in nasal fluid and sera or plasma.
 - c. Increased serum IgE-inhibitory activity (assessed by IgE-FAB in sera or plasma and IgE-mediated basophil activation in whole blood).

Depending on sample and technology available, additional fluids/cells may be used to test the hypotheses described above.

9.2 PROPOSED MECHANISTIC ASSAYS

Although specimens in this protocol are described in the context of assays to be performed, it should be noted that not necessarily all assays will be performed for all participants at each time point. Decisions to perform assays will be made based on statistical and scientific planning, hypotheses to be tested, and technologies available. Finally, clinical outcomes will be taken into account to determine the potential value of the assays. For example, if a clinical effect fails to occur, it may be decided that there is minimal value in performing certain mechanistic assays. The ITN sample sharing policy will apply for the provision of samples to study or outside investigators (www.immunetolerance.org).

Residual stored specimens may be used by the investigators for development of new immunologic assays or for cross-trial comparisons. Use of de-identified samples for novel assays will be submitted to the National Research Ethics Committee (NREC) for approval. The use of these de-identified samples will not require additional consent by participants.

9.2.1 LOCAL IMMUNE RESPONSES IN NASAL MUCOSA

Nasal fluid and epithelial brushings will be collected as listed in Appendix 1, 2 and 5.

Nasal fluid will be collected for protein analysis. Analytes to be measured in nasal fluid may include Th2 cytokines (IL-4, 5, and 13), Th1-cytokines (IFN- γ , IL-12, IL-27, and IFN- α), and regulatory cytokines (IL-10, TGF- β , and IL-35). Th2-related chemokines (MDC, TARC, and eotaxin), Th1-related chemokines (IP-10), and other inflammatory mediators may also be measured. In addition, local IgE-FAB inhibitory activity may be assessed and grass pollen-specific antibody levels (IgE, IgA, IgG and IgG4) may be measured in nasal fluid by ImmunoCAP or ELISA.

Nasal epithelial cells will be harvested by gently brushing the nasal inferior turbinates and RNA extracted. To avoid interfering with nasal fluid collections, nasal brushes will only be taken after nasal fluid has been collected. Gene expression may be assessed by methods such as RT-PCR, RNAseq, or nanostring for comparisons between treatment arms. Specific genes targeted for RT-PCR analysis may include genes for epithelial cell-derived chemokines (MDC, TARC, eotaxin, RANTES), adhesion molecules (ICAM-1), and cytokines such as IL-8, GM-CSF and those that may possibly be detected in trans-epithelial migratory effector cells (IL-4, IL-5, IL-9, IL-13, Interferon-gamma, IL-10 and TGF-beta). Transcription factors of interest could include GATA-3, STAT-6, T bet, and FOXP3. Epithelial Th2-inducing cytokines of interest could include IL-25, IL-33 and TSLP.

9.2.2 DNA-HLA GENOTYPES

Major Histocompatibility Complex (MHC) tetramers bind to the T-cell receptor in a Human Leukocyte Antigen (HLA) specific context. Therefore, DNA will be collected from participants to perform sequence-based HLA typing, such that appropriate candidates can be identified for tetramer analysis.

Additional genotyping (e.g. IL-4R alpha polymorphisms) may be performed in order to determine whether genetic profiles are associated with response to grass pollen immunotherapy or other study characteristics.

9.2.3 WHOLE BLOOD GENE EXPRESSION

Gene expression profiling may be performed on RNA isolated from peripheral whole blood using RNAseq, nanostring, RT-PCR, or other methods. The goal of these assays is to identify differences in transcriptional profiles between treatment arms and clinical outcome groups, and to monitor the durability of these potential changes after discontinuation of immunotherapy. These types of analyses may also explain why some individuals respond to treatment or may elucidate mechanisms resulting in adverse responses to treatment. Changes in whole blood gene expression could also be compared and contrasted with local (nasal) gene expression changes.

9.2.4 CELLULAR ASSAYS

T Cell Assays: To address the functional status of T-cell responses, various cell-based assays using previously frozen PBMCs can be used to estimate frequency, phenotype, cytokine, and transcriptional profile of allergen-specific cells.

MHC Class II tetramers may be used to identify & enumerate grass allergen-specific CD4 T cells using flow cytometry or CyTOF. Additional staining of surface markers may be performed to determine if treatment leads to the development of anergy, exhaustion, Th2 to Th1 deviation, or the induction of regulatory T cells.

Since tetramers are not currently available for all haplotypes, other T cell assays may also be performed. The CD154 and CD137 up-regulation assays may be used to monitor allergen-reactive effector and regulatory CD4 T cells, respectively with either flow

cytometry or CyTOF. Currently, these assays require PBMCs to be stimulated *in vitro* with grass allergen in the presence of anti-human CD40 blocking mAb. If flow cytometry is used, during acquisition, cells may be sorted and epigenetic or transcriptomic studies performed on the allergen-specific effector and regulatory cells.

The CD154 up-regulation assay can also be performed to measure cytokine production in allergen-specific CD4 cells. Intracellular staining for IL-4, IL-5, IL-13 and IFN- γ (Th1/Th2), IL-17 (Th17), along with IL-10 and TGF- β (Th3) could be performed and combined with surface staining to assess changes in effector CD4 subpopulations.

We may also use flow cytometry or CyTOF to determine the frequency of TH2A cells as this subset of Th2 cells may be a biomarker for allergy.⁶¹ This assay can be reliably performed with as few as one million previously frozen, viable PBMCs. Work by Wambre, et al suggests that this subset includes the vast majority of allergen-specific CD4+ T cells as determined by tetramer analysis.⁶¹

The FluoroSpot assay could also be used to further explore the phenotype and evaluate the frequency of cytokine-producing antigen-specific cells. The FluoroSpot assay requires 18–48 hours of cell stimulation with allergen (*Phleum pratense* component proteins or whole *Phleum pratense* grass extract) and reveals frequencies of antigen-specific cells producing cytokines of interest, such as IL-4, IL-5, and IL-10. Therefore, it represents an additional functional readout of T-cell activity.

Whole Blood IgE-dependent Basophil Activation: IgE-dependent basophil activation will be assessed using fresh whole blood incubated with different concentrations of *Phleum pratense* allergen extract. Basophil surface CD63 expression will be monitored by flow cytometry to determine basophil activation levels.

Other Immune Cells: Using flow cytometry or CyTOF, we may perform detailed immunoprofiling of other cell types such as B cells, NK cells, dendritic cells, and others.

9.2.5 SERUM/PLASMA ASSAYS

Cytokines/Chemokine Assays: Whole blood (10 ml) will be collected as outlined in Appendices 1, 2, and 5 coincident with corresponding nasal fluid collections for measurement of Th2, Th1, regulatory and other cytokines/chemokines. ELISA, single-molecule digital immunoassays, or other methods may be used to measure levels of cytokines, chemokines and other inflammatory mediators in/out of season or elicited following a NAC.

Immunoglobulin assays: Serum antibody responses may be measured to determine levels of total and allergen-specific antibodies. These measurements could include testing for total IgE and IgG and allergen-specific IgE, IgG1, IgG4, IgA1 and IgA2. IgG1, IgG4, and IgA may be induced by immunotherapy and may act as blocking antibodies reducing clinical responses to allergen.

Component-resolved assays: ImmunoCAP™ may be used to measure levels of antibodies to *Phleum pratense* components. Levels of IgE, IgG4, and IgA to specific grass allergen components, such as *Phl p* 1, 2, 4, 5, 6, 7, 11, and 12 may be measured to evaluate changes in specific reactivity over time and between treatment arms.

IgE-facilitated antigen binding (FAB) assay: In addition to antibody testing, serum samples may be used in functional assays to measure serum inhibitory activity. The IgE-FAB inhibition assay uses flow cytometry to measure serum inhibitory activity of IgE-facilitated CD23-dependent binding of allergen-IgE complexes to B cells. Serum from SLIT plus dupilumab placebo, combination of SLIT and dupilumab, and double placebo arms may be assessed for its inhibitory activity for IgE-FAB. The time course and magnitude of changes in inhibitory activity for IgE-FAB may be compared with clinical symptoms, clinical scores, and allergen-specific IgE and IgG levels.

10. BIOSPECIMEN STORAGE

A major priority of the ITN, in partnership with the NIAID of the National Institutes of Health (NIH), USA, is the development of novel immunoassays in order to better understand mechanisms of tolerance and to develop biomarkers to predict the development and maintenance of clinical tolerance. As in all ITN-funded clinical trials, informed consent will be obtained from all participants for their samples to be stored for use in future studies. Biological specimens collected in this trial will be stored long-term in order to re-evaluate biologic responses as new research tools to study tolerance become available. The specimens will therefore be stored at the ITN sample repository for a minimum of 10 years. For research on stored samples that has not been defined in the protocol, approval from the relevant ethics committee will be obtained.

11. CRITERIA FOR PARTICIPANT AND STUDY COMPLETION AND PREMATURE STUDY TERMINATION

11.1 PARTICIPANT COMPLETION

Participants will have completed the study when they have attended the S15 Visit for mechanistic blood collection and skin prick test endpoint titration.

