3. STUDY DESIGN

3.1 DESCRIPTION OF THE STUDY DESIGN

This is a randomized, double blinded trial in adults (n=108) with moderate to severe seasonal allergic rhinitis with allergic sensitization to grass pollen.

During the screening visit, participants will be asked for demographic information, complete a brief questionnaire concerning their allergic rhinitis, severity and duration, and impact on their quality of life, work or school performance and sleep. Any co-morbidities including asthma, eczema, or sinusitis; their past medical history; smoking history and medication history will be recorded. Participants will undergo skin prick testing with a panel of inhaled aeroallergens and with positive and negative controls. A blood sample will be taken for full blood count, total and specific IgE to grass and tree pollen, comprehensive chemistry and liver function tests.

[figure not shown]
Participants who meet eligibility criteria and choose to enroll will undergo a baseline visit. Thereafter participants will be randomized 1:1:1 to three parallel treatment arms as follows:

- Combination of SLIT and dupilumab (n=36)
- SLIT plus dupilumab placebo (n=36)
- SLIT placebo plus dupilumab placebo (i.e. double-placebo) (n=36)

Grazax[®] is a sublingual grass immunotherapy product approved for clinical use in the United Kingdom and will be used as SLIT in this study. It (and its matching placebo) will be self-administered daily by participants through week 104. Dupixent[®] is the brand name for dupilumab and is a monoclonal antibody against the IL-4 receptor. Dupilumab and its placebo will be administered every two weeks by subcutaneous injection through week 104. With appropriate training by study personnel, alternate doses of dupilumab (and other occasional doses as required) may be self-administered by participants at home. Dupilumab is approved for self-administration by patients. The treatment phase of 104 weeks will be followed by an observation phase of 52 weeks.

[figure not shown]
A NAC will be performed at baseline (Visit -1) and repeated annually after 1 and 2 years of study treatment and at 3 years (1 year after completion of study treatment). Annual NACs should be done at the same time every year, within +/-14 days of the preceding year's NAC. Blood, nasal brushings, and nasal fluid samples will be collected as outlined in Appendices 1 through 5.

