8.5 VISIT WINDOWS

All scheduled study visits will aim to occur within the time limits specified below and may be adjusted based on pollen count and participant availability.

Table 7. Visit Windows all Participants (See Appendices 1-5)

Visit	Visit description	Visit Window
Visit -4	Screening	October 2020 to January 2022
Visit -3	Rescue medication dispensing visit	April 1 to July 31
Visit -2	Baseline In-season assessments	June 1 to July 31
Visit -1	Baseline NAC	September to January
Visit 0	Randomization – 1 st dupilumab/dupilumab placebo dose	≥ 28 days after Visit -1 and before end of February
Visit 1	1 st SLIT/SLIT placebo dose	≥12 hours from Visit 0 and ≥ 7 days prior to Visit 2.
Visits 2-53	Treatment visits	Every 2 weeks from Visit 0 through week 104 +/- 10 days (with at least 7 days between treatment visits)
Visits 54-65	Observation visits	Every 4 weeks from 108 to 156 +/- 14 days
S1	Out of season visit assessment year 1	January to April
S2, S7, S12	Pre-season visit	April to May
S3, S8, S13	In-season visits	May to August
S4, S9, S14	Out-of-season NAC visits	September to January 1, 2 and 3 calendar years after Visit -1 +/- 14 days
S5, S10, S15	Mechanistic draws post NAC visits	≥ 4 weeks post NAC visit (S4, S9, S14) and before end of February each year
S6, S11	Out of Season visit	January to April

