12.4 COLLECTION AND RECORDING OF ADVERSE EVENTS

12.4.1 COLLECTION PERIOD

AEs/SAEs within 24 hours of study procedures will be collected during the screening period (visits -4 to visit -1). After the screening period, all AEs/SAEs will be collected from participants who undergo a baseline NAC (visit -1) until he/she completes study participation or until 30 days after he/she prematurely withdraws (without withdrawing consent) or is withdrawn from the study.

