10.2. Extent of Exposure

No other summaries for exposure will be created other than the treatment compliance summaries per [Section 7.3](#) above.

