Summary tables will present the total number of events, as well as the number and percentage of participants experiencing the events. If a participant experiences the same AE on multiple occasions, the event will be counted for each occurrence when reporting the number of events. When reporting the number of participants experiencing the events, a participant will only be counted once if they experience an event within the particular SOC or PT. Percentages will be based on the number of participants in the analysis sample of interest.

In addition to the above treatment-emergent summaries at any time post-treatment, AEs will be summarized during year 1, 2, and 3 separately using the following displays:

- Overall summary (repeated with same categories as above)
- Any AE by SOC/PT
- AEs by maximum severity (all severity grade criteria combined)
- SAEs by maximum severity (all severity grade criteria combined)
- AEs by relationship to study drug

For the above AE year intervals, the analysis windows are as follows for counting events:

Year Interval	Lower Bound	Upper Bound
Year 1 (Week 0 through <Week 54)	Study Day 1 (first treatment date)*	Study Day 377
Year 2 (Week 54 through < Week 108)	Study Day 378	Study Day 755
Year 3 (Week 108 onwards)	Study Day 756	No upper bound

*Study day is defined per [Section 8](#) of this SAP.

The denominators for percentages will be for each time interval as follows:

Year Interval	Denominator Subset
Year 1 (Week 0 through <Week 54)	All participants in the Safety sample
Year 2 (Week 54 through < Week 108)	All participants in the Safety sample who remained in the study through Study Day 378
Year 3 (Week 108 onwards)	All participants in the Safety sample who remained in the study through Study Day 756

The study day for inclusion for denominators will be based on the maximum of 1.) end of study date, 2.) date of most-recent follow-up, and 3.) last AE start date.

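### Completion at S15 runs on a different clock from the 52-week observation phase, so scheduled off-treatment AE follow-up can stop early; separately, the SAP's yearly AE percentages are not comparable across years

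*Protocol*

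**What the plan says.** **When participation ends.** Protocol 11.1: "Participants will have completed the study when they have attended the S15 Visit for mechanistic blood collection and skin prick test endpoint titration". No minimum week is attached. Protocol 12.4.1 ties AE collection to that event: "all AEs/SAEs will be collected from participants who undergo a baseline NAC (visit -1) until he/she completes study participation", or until 30 days after early withdrawal.

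**When S15 happens.** In the visit-window table of Protocol 8.5 (Table 7), Visit -1 falls in "September to January". Visit 0 follows at least 28 days later and before the end of February. The year-3 challenge (S14) is set three calendar years after Visit -1, within 14 days either way. S15 comes at least 4 weeks after S14 and before the end of February.

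**How long observation lasts.** Protocol 3.1: "The treatment phase of 104 weeks will be followed by an observation phase of 52 weeks". Weeks are counted from Visit 0. The 8.5 table times observation Visits 54 to 65 as "Every 4 weeks from 108 to 156 +/- 14 days". Appendix 4 lists the same twelve visits as phone calls at weeks 108 to 152, with AEs marked at every one.

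**How year 3 is reported.** SAP 10.3 counts AEs in year 1 (study days 1 to 377), year 2 (days 378 to 755) and year 3 (day 756 onwards, no upper bound). The year-3 denominator is "All participants in the Safety sample who remained in the study through Study Day 756". On exposure, SAP 10.2 says: "No other summaries for exposure will be created other than the treatment compliance summaries".

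**The concern.** Two clocks govern the end of follow-up. Treatment, the observation phase and the AE calls count from Visit 0. S14, S15 and therefore completion count from Visit -1. The longer the gap between those two visits, the earlier S15 falls on the week scale, and nothing in the protocol says whether the remaining calls go ahead once S15 has been attended. A site applying 11.1 and 12.4.1 as written would stop them. Year-3 AEs are a named part of the safety endpoint, so what is at stake is off-treatment safety follow-up that is already scheduled.

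The second matter is how the yearly tables read. They set percentages of participants side by side for windows of different length, and year 3 has no fixed length. Part of any fall or rise from year 2 to year 3 would reflect days observed rather than event rate.

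**Working it through.** **Stated figures reproduce.** 104 + 52 = week 156, the upper limit in the 8.5 table. Twelve visits every 4 weeks from week 108 end at 108 + 4 × 11 = week 152, as in Appendix 4. The two places therefore differ by one 4-week step. In the SAP, 54 × 7 = 378 and 108 × 7 = 756, matching its year boundaries.

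**S15 on the week scale.** Let g be the days from Visit -1 to Visit 0, e the deviation of S14 from its anniversary (-14 to +14), and h the days from S14 to S15 (at least 28). Three calendar years from autumn 2021 are 1,096 days.

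- Days from Visit 0 to S15 = 1096 + e + h - g.
- Days from the planned last dose (week 104, 728 days) to S15 = 368 + e + h - g.
- The range of g is 28 days to 180 days (1 September to 28 February).

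With e = 0 and h = 28, S15 precedes week 152 (1,064 days) when 1124 - g < 1064, that is g > 60.

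| g (days) | S15 at week (e = 0, h = 28) | Year-3 AE days to S15 |
|---|---|---|
| 28 | 156.6 | 342 |
| 56 | 152.6 | 314 |
| 90 | 147.7 | 280 |
| 120 | 143.4 | 250 |
| 150 | 139.1 | 220 |
| 180 | 134.9 | 190 |

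Year-3 AE days are (days from Visit 0 to S15) + 1 - 755.

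**Extremes.** Earliest: 1096 - 14 + 28 - 180 = 930 days, week 132.9, which is 202 days after the planned last dose and before 5 of the 12 calls (weeks 136 to 152). This puts S14 in mid-August. If S14 may not precede September, it is 944 days, week 134.9, or 216 days after the planned last dose. Latest: Visit -1 on 1 September, Visit 0 28 days later and S15 on 28 February give 1,248 days, about week 178.

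**SAP window lengths.** Year 1 has 377 days and year 2 has 755 - 377 = 378. Year 3 has 1064 + 1 - 755 = 310 days if follow-up ends at week 152, and 1092 + 1 - 755 = 338 if it ends at week 156. With S15 as the end it runs from 176 days (190 with a September limit) to 494. The planned week-104 dose is study day 729, so year 2 also contains 755 - 729 = 26 days after it.

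**Effect on percentages (illustration).** Assume a constant event rate and a share p with at least one AE in 378 days. The expected share in d days is 1 - (1 - p)^(d/378). The documents give no AE rate, so three values of p are shown.

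| Days observed | p = 20% | p = 40% | p = 60% |
|---|---|---|---|
| 378 | 20.0% | 40.0% | 60.0% |
| 338 (week 156) | 18.1% | 36.7% | 55.9% |
| 310 (week 152) | 16.7% | 34.2% | 52.8% |
| 190 | 10.6% | 22.6% | 36.9% |
| 176 | 9.9% | 21.2% | 34.7% |
| 494 | 25.3% | 48.7% | 69.8% |

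**The case against.** **Follow-up may not be lost at all.** A reader might infer that the protocol discards off-treatment safety data. The 8.5 table is headed as applying to all participants and schedules the observation visits; Appendix 4 marks AEs at each; nothing says the calls stop after S15. This stands. What the text shows is a contradiction between 11.1 with 12.4.1 and the week-based schedule, and early stopping follows only on a literal reading.

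**The share affected is unknown.** If Visit -1 and Visit 0 are assumed uniform over their windows, S15 precedes week 152 in 46% of schedules with a 4-week lag, 34% with a lag of 4 to 8 weeks, and 15% if S15 is spread evenly to the end of February. The documents support none of these distributions, so no share should be claimed. Week 133 needs the longest gap, the shortest lag and a mid-August S14 all at once.

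**S15 is not the main reason year 3 is short.** A reader might attribute the whole shortfall to S15. Full follow-up to week 152 or 156 still gives only 310 or 338 days, because the SAP makes years 1 and 2 54 weeks each. Nor is year 3 shorter for everyone: a late S15 takes it past 378 days. Both points stand.

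**SAP 10.2 does not forbid a time-at-risk summary.** It concerns extent of drug exposure. SAP 6.1 lists first dose, last visit and termination dates, so follow-up time is recoverable. It is simply not planned as a denominator.

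**The consequence is limited.** The safety analysis is descriptive by arm and no test between years is planned. Years also differ in treatment status and in frequency of contact, so person-year rates will not make a year-to-year reading clean. They do remove the part due to unequal observation time.

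**Conclusion.** The concern holds in two limited parts.

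First, the completion and AE-collection rules contradict the week-based observation schedule. With S14 on its anniversary and S15 28 days later, any Visit -1 to Visit 0 gap over 60 days puts S15 before the week-152 call. At the extreme, S15 falls at about week 133 (week 135 with a September limit on S14), leaving 202 or 216 days after the planned last dose against a stated 52 weeks. This rests on a literal reading of 11.1 and 12.4.1; how many participants are affected cannot be derived from the documents.

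Second, the yearly AE percentages in SAP 10.3 are not comparable across years, mainly because years 1 and 2 are 54 weeks long and additionally because S15 timing makes year 3 uneven. At a constant rate giving 40% in 378 days, year 3 would show about 34% to 37% with follow-up to week 152 or 156, and between about 21% and 49% at the extreme S15 dates.

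A reader might go on to infer bias between arms. The documents do not support that: the Visit -1 to Visit 0 gap is settled by the time of randomisation, and later visit timing is under double-blind conditions.

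**What to change.** **Protocol 11.1 and 12.4.1.** Reconcile them with the observation schedule by defining completion as the later of S15 and the last scheduled observation phone visit. Give that visit the same week in the 8.5 table and in Appendix 4.

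**SAP 10.3.** Add days at risk and AEs per person-year, by arm, to the year 1, 2 and 3 tables. Footnote that the year-2 window includes about 4 weeks after the planned last dose. Leave the year-2 cut-off where it is: treatment visits have a window of 10 days either way, so a cut at week 104 could place events around a late final dose in the off-treatment year.

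**Cost.** One sentence in the protocol, one aligned week number, and a few columns built from dates already collected. Some participants stay on the call list for some weeks after S15, up to about 152 - 133 = 19 weeks to week 152 in the extreme case. The note appended to the SAP refers to database lock as past. For this trial the reporting change therefore remains feasible, while the completion rule can only be clarified by stating how it was applied.
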